8.3 Definition of Baseline

Baseline measures are defined as the last measure prior to the initiation of study treatment. Change from Baseline will be calculated as Follow-up Visit – Baseline Visit.

8.4 Data Analysis Conventions

All data analyses will be performed by SDC after the study is completed and the database has been locked and released for unmasking. Statistical programming and analyses will be performed using SAS® version 9.4 or higher. Output will be provided in rich text format (RTF) for tables and portable document format (PDF) for tables, listings, and figures using landscape orientation.

Summaries for continuous and ordinal variables will include the number of observations (n), arithmetic mean, standard deviation (SD), median, minimum, and maximum. Minima and maxima will be reported with the same precision as the raw values; means and medians will be presented to one additional decimal place than reported in the raw values. Standard deviations will be presented to two additional decimal places than reported in the raw values. Summaries for discrete variables will include counts and percentages. All percentages will be rounded to one decimal place (i.e., XX.X%). Differences between the active treatment group and placebo will be calculated as active minus placebo.

All statistical tests will be one-sided with a significance level of 0.025 ($\alpha = 0.025$) unless otherwise specified. Confidence intervals (CI) for differences between treatment groups as well as change from baseline will be two-sided at 95% confidence. All p-values will be rounded to 4 decimal places; p-values less than 0.0001 will be presented as “<0.0001”; p-values greater than 0.9999 will be presented as “>0.9999.”

Unless otherwise specified, summaries will be presented by treatment group and, where appropriate, visit. Listings will be based on all randomized subjects unless otherwise specified, and sorted by subject number, visit/time point, and parameter as applicable.

8.5 Adjustments for Multiplicity

A closed hierarchical testing structure will be used where the analysis will be performed for the primary efficacy endpoint, and, only if successful, the analysis will be performed for the two secondary efficacy

endpoints using the Hochberg testing strategy. Specifically, if the null hypothesis, H_{01} , is rejected at a one-sided α of 0.025, the study will be considered a success for clinical cure and the two secondary efficacy endpoints will be tested using the Hochberg testing strategy with an α of 0.025. If the null hypothesis, H_{01} is not rejected at a one-sided α of 0.025, testing will stop and the two secondary efficacy hypotheses will be deemed not statistically significant.

9. Disposition of Subjects

Subject disposition will be presented in terms of the numbers and percentages of subjects who were randomized to masked study medication with subcategories of dosed with the masked study medication, did not dose with masked study medication; who were included in the following analysis populations: FAS, PP set, safety set; and who completed the study and discontinued from the study. Subjects who are not discontinued from the study will be considered study completers. Disposition will be summarized by treatment group and for all subjects. Subject enrollment and disposition will be summarized by treatment group and site. Percentages will be calculated using randomized subjects as the denominator unless otherwise specified.

The reasons for premature study discontinuation will be summarized by treatment group for all discontinued subjects. Percentages will be calculated using randomized subjects as the denominator. The reasons for study discontinuation that will be summarized include: AE, significant study treatment non-compliance per PI determination, pregnancy, exclusion criteria, reasons relating to COVID-19, and other. A subject listing will be provided that includes the date of and reason for premature study discontinuation.

The number and percentage of subjects with any deviation, major deviation, and minor deviation will be summarized by treatment group for all randomized subjects. The protocol deviations that will be summarized include the following categories: informed consent, inclusion/exclusion and Randomization, test article/study drug instillation and assignment at site, improper protocol procedures at site, site's failure to report SAE/AE, visit out of window (missed, early, late), subject's non-compliance with test article, subject's use of prohibited concomitant medication, subject's failure to follow instructions, COVID-19: visit missed, COVID-19: assessment not performed, COVID-19: other, or other. A subject listing will be provided that includes the date of the deviation, the deviation category, the deviation description, classification of whether the deviation was judged to be COVID-19 related, and the classifications of whether the deviations were judged to be major or minor and potential impact on the primary efficacy endpoint based on a masked review.

In addition, subject listings will be provided that include informed consent date, inclusion and exclusion criteria violations, and exclusions from the PP set. Details of the study randomization, including randomization date, randomized treatment and actual treatment, will also be included within a subject listing.

10. Demographic and Pretreatment Variables

10.1 Demographic Variables

The demographic variables collected in this study include age, sex, child-bearing potential, race, ethnicity, and iris color (OD and OS). Demographic variables will be summarized for the FAS, COVID-19 Analysis Set, PP set, and safety set, separately. Demographic variables will be summarized by site for the FAS.

Age (years) will be summarized, overall and by treatment, using continuous descriptive statistics as well as dichotomized into age <65 years and age ≥65 years. Age will be reported in years and calculated using the age at last birthday.

The number and percentage of subjects will be presented, overall and by treatment, for sex, childbearing potential, race, ethnicity, and iris color (OD and OS).

A subject listing that includes all demographic variables will be provided.

11. Medical History and Concomitant Medications

11.1 Medical History

Medical history will be coded using the Medical Dictionary for Regulatory Activities (MedDRA) version 23.0.

Ocular medical history will be summarized using discrete summary statistics and presented by treatment group at the subject level by System Organ Class (SOC) and Preferred Term (PT) using the safety set. Non-ocular medical history will be similarly summarized at the subject level. Medical history will be summarized by PT and SOC at the subject level. A subject will only be counted once even if they have multiple histories for a given classification. Summaries will be sorted in decreasing frequency.

Listings of medical history will be generated separately for ocular and non-ocular data.

11.2 Concomitant Medications

Concomitant medications will be coded using World Health Organization Drug Dictionary (WHO DRUG) Global (B3, March 2020) and summarized to the therapeutic drug class (Anatomical Therapeutic Chemical [ATC] 4 classification) and preferred name. If the ATC 4 classification is not provided, the next lowest classification that is provided in the coding dictionary will be used. The preferred name will be defined as the active ingredient; if the active ingredient is not provided or includes more than two ingredients (e.g., multivitamins) then the drug name will be summarized as the preferred name.

Concomitant medications are defined as those medications listed as having been taken (1) prior to initiation of study drug administration and continuing for any period of time following the first administration of study drug or (2) at any time following the first administration of study drug.

Concomitant medications will be summarized using the safety set. Medications will be tabulated for each treatment group using frequencies and percentages. Subjects may have more than one medication per ATC text. At each level of subject summarization, a subject will be counted once if he/she reports one or more medications. Percentages will be based on the number of subjects in each treatment group.

Summaries will be sorted in decreasing frequency. Listings of concomitant medications will be generated separately for ocular and non-ocular data, including indication, route of administration, start date, and end date or ongoing.

11.3 Concomitant Procedures

Concomitant procedures will be coded using the Medical Dictionary for Regulatory Activities (MedDRA) version 23.0 and summarized by SOC and PT.

Concomitant procedures will be summarized using the safety set. Procedures will be tabulated for each treatment group using frequencies and percentages. Subjects may have more than one procedure per PT. At each level of subject summarization, a subject will be counted once if he/she reports one or more procedures. Percentages will be based on the number of subjects in each treatment group. Summaries will be sorted in decreasing frequency. Listings of concomitant procedures will be generated separately for ocular and non-ocular data.

12. Dosing Compliance

12.1 Dosing Compliance

Dosing compliance (% compliance) will be assessed by calculating the number of actual doses received and comparing that to the number of expected doses as follows:

$$\text{Compliance (\%)} = \frac{\text{Number of Actual Doses Received} \times 100\%}{\text{Number of Expected Doses}}$$

The number of actual doses received will be recorded in the CRF (first dose in Study Drug Instillation CRF and remaining doses in Study Drug Diary CRF). Two doses are expected each day except only one dose should be completed on the last day of the study. The number of expected doses that will be used for calculating compliance will be calculated as:

$$2 \times (\text{Date of Last Dose} - \text{Date of First Dose}) + 1$$

for all subjects, regardless of study completion status.

A categorical dosing compliance variable will also be derived as non-compliant (<80%), compliant ($\geq 80\%$ and $\leq 125\%$), and over compliant ($>125\%$).

Dosing compliance (%) will be summarized with continuous descriptive statistics for each treatment group, as well as by site, sex, age, and race using the safety set. The compliance category defined above will be summarized with discrete summary statistics.

A subject listing of dosing compliance will also be produced.

13. Efficacy Analyses

The efficacy assessments performed include the following:

- Assessment of collarette grade
- Assessment of erythema grade
- Eyelash epilation and mite counts

Collarette grade is determined based on number of lashes with collarettes per eyelid (Table 3). The proportion of subjects cured in the upper eyelid of the analysis eye based on collarette grade will be summarized by visit and treatment group. The percentage of subjects at each grade will be summarized by visit and treatment group, as well as by site, sex, age, and race. The proportion of subjects cured in the upper eyelid of the analysis eye by visit and treatment group will be displayed graphically by bar charts.

Table 3. Collarette Grading

Grade	Clinical Interpretation
0	0 to 2 lashes have collarettes per eyelid
1	3 to 10 lashes have collarettes per eyelid
2	More than 10 but less than $\frac{1}{3}$ of lashes have collarettes per eyelid
3	$\frac{1}{3}$ or more but less than $\frac{2}{3}$ of lashes have collarettes per eyelid
4	$\frac{2}{3}$ or more of lashes have collarettes per eyelid
0.5 unit increments ARE NOT allowed	

The observed value and change from Baseline in collarette score will be summarized by visit and treatment group. Erythema of the eyelid margin is graded on a scale from 0 (normal) to 3 (severe erythema) (Table 4). The percentage of subjects at each grade level in the upper eyelid of the analysis eye will be summarized by visit and by treatment group, as well as by site, sex, age, and race. The change from baseline in mean collarette score and in mean erythema score in the upper eyelid of the analysis eye by visit and treatment group will be displayed graphically by bar charts.

The proportion of subjects composite cure based on collarette and erythema scores will be summarized by visit and by treatment group, as well as by site, sex, age, and race. The proportion of subjects with composite cure in the upper eyelid of the analysis eye by visit and treatment group will be displayed graphically by bar charts.

Table 4. Lid Margin Erythema Grading

Grade	Severity	Clinical Interpretation
0	Normal	Normal age-related lid coloration
1	Mild	Pink capillary involvement along the lid edge, no patches of confluent capillary redness throughout the lid edge
2	Moderate	Deep pink or red confluent capillary redness present locally along the lid edge
3	Severe	Deep red, diffuse confluent capillary redness present along the lid edge
0.5 unit increments ARE NOT allowed		

Mite density in the analysis eye and change from Baseline will be summarized by visit and treatment group, as well as by site, sex, age, and race. The proportion of subjects with *Demodex* eradication will be

summarized by visit and treatment group, as well as by site, sex, age, and race. The proportion of subjects with *Demodex* eradication and change from baseline in mean mite density in the upper eyelid of the analysis eye by visit and treatment group will be displayed graphically by bar charts.

13.1 Primary Analysis

The primary efficacy endpoint is cure based on collarette score of 0 for the upper eyelid of the analysis eye at Day 43. The primary efficacy endpoint will be conducted on the FAS, with intercurrent events handled as described in Section 8.2. Descriptive statistics will be presented by treatment arm. Testing of the percentage of subjects cured at Day 43 based on the collarette grade will be completed using a difference of proportions test.

As specified in Section 8.2, missing data without withdrawal or withdrawal due to reasons other than lack of efficacy or AEs will be imputed employing MI using randomized treatment-based MCMC methodology.

The following SAS code will be used to generate the multiple imputation datasets:

```
PROC MI DATA=INDATA SEED=56636 NIMPUTE=20 OUT=OUT1 MINIMUM=0 MAXIMUM=4 ROUND=1;
  BY TRT;
  MCMC INITIAL=EM;
  VAR BASE DAY08 DAY15 DAY22 DAY43;
RUN;
```

The multiple imputation datasets will be used to calculate cure based on a collarette score of 0 at Day 43. The following SAS code will then be used to calculate the difference of proportions for each imputed dataset and combine the analyses across imputations:

```
PROC SORT DATA=OUT1; BY _IMPUTATION_; RUN;
PROC FREQ DATA=OUT1;
  BY _IMPUTATION_ ;
  TABLES TRT*CURE / RISKDIFF CL;
  ODS OUTPUT RISKDIFFCOL2=PROP;
RUN;
PROC MIANALYZE DATA=PROP;
  WHERE ROW='Difference';
  MODELEFFECTS RISK;
  STDERR ASE;
  ODS OUTPUT PARAMETERESTIMATES=PEST;
RUN;
```

Statistical comparison between treatment groups will be one-sided using an α of 0.025.

In addition to the primary analysis, supplementary analyses are proposed under different assumptions for the estimand to assess efficacy in patients who have missing data.

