A total sample size of 300 subjects (150 subjects per arm) yields approximately 99% power to establish superiority of TP-03 to vehicle in the subjects meeting the primary efficacy endpoint assuming a response rate of 80.0% in TP-03 and 15.8% for vehicle treatments, respectively using a Pearson chi-squared test with a one-sided significance level of 0.025. Response rates for sample size calculations are based upon a prior outside United States clinical study of TP-03, 0.25%, and vehicle for the treatment of *Demodex* blepharitis.

Similarly, 300 subjects (150 subjects per arm) yields 99% and 99% power to establish superiority of TP-03 to vehicle treatment in the proportion of subjects with *Demodex* eradicated and the proportion of subjects with a composite of collarette and erythema cure respectively at Day 43 assuming a response rate of 73.3% in TP-03 and 21.1% in vehicle and 73.3% in TP-03 and 10.5% in vehicle using a Pearson chi-squared test with a one-sided significance level of 0.025.

The study will be considered a success and TP-03, 0.25%, will be considered superior to vehicle in clinical cure if H_{01} is rejected in favor of H_{11} . With this sample size, the study will have > 95% power to claim success for clinical cure. If in addition to success for clinical cure, H_{02} is rejected in favor of H_{12} , the study will also claim superiority of TP-03, 0.25%, to vehicle in *Demodex* eradication. Similarly, if in addition to success for clinical cure, H_{03} is rejected in favor of H_{13} , the study will also claim superiority of TP-03, 0.25%, to vehicle in composite collarette and erythema cure. With this sample size, the study will have > 95% power to claim success for clinical cure and superiority for both *Demodex* eradication and collarette and erythema cure.

Accounting for a 30% discontinuation, approximately 209 subjects per arm (approximately 418 total) will be randomized. The planned enrollment is much greater than typically planned to achieve 300 completed subjects due to concerns regarding the impact of COVID-19, and the possibility that up to two sites may be unable to complete the study.

6. Data Preparation

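### The primary risk difference is valid but makes no use of baseline collarette grade in the treatment comparison; stratifying by it would narrow the interval at almost no cost

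*SAP*

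**What the plan says.** The primary endpoint is a collarette score of 0 on the upper eyelid of the analysis eye at Day 43. SAP Section 13.1 sets the test: "Testing of the percentage of subjects cured at Day 43 based on the collarette grade will be completed using a difference of proportions test". In the code this is "TABLES TRT*CURE / RISKDIFF CL", run within each imputed dataset and pooled with PROC MIANALYZE. It has no stratum or covariate.

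The imputation step ("PROC MI DATA=INDATA SEED=56636 NIMPUTE=20 OUT=OUT1 MINIMUM=0 MAXIMUM=4 ROUND=1") is run by arm with "VAR BASE DAY08 DAY15 DAY22 DAY43", so baseline grade helps to fill in missing Day 43 grades. Table 2 of the SAP shows collarette grading at Screening.

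None of Sensitivity Analyses I to V adds a baseline-adjusted comparison of the arms. SAP Section 4.2 describes blocked 1:1 randomization, and the visible text names no stratification factor. SAP Section 13.2 reuses the same code for both secondary endpoints.

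SAP Section 5 sizes the trial on an unadjusted basis: "A total sample size of 300 subjects (150 subjects per arm) yields approximately 99% power", "assuming a response rate of 80.0% in TP-03 and 15.8% for vehicle treatments", "using a Pearson chi-squared test with a one-sided significance level of 0.025".

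**The concern.** Cure means reaching an absolute level, at most two lashes with collarettes (SAP Table 3). SAP Section 2 describes the disease under study as mild to severe. A subject who starts with collarettes on two-thirds of the lashes has further to go than one who starts just above ten lashes, so baseline grade plausibly predicts cure. The plan treats it as informative by imputing from it.

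If baseline grade does predict cure, the crude comparison gives a wider confidence interval than the data require. The point estimate also carries any chance imbalance in baseline grade, which neither the visible randomization scheme nor the comparison controls. At stake are the width of the reported 95% interval and the ease of defending the estimate if the arms differ at baseline. The validity of the test is not at stake.

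**Working it through.** **1. The plan's own figure.** Inputs from SAP Section 5: n = 150 per arm, p1 = 0.80, p0 = 0.158, one-sided α = 0.025.

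Power = Φ{[(p1 − p0)√n − 1.96·√(2p̄(1 − p̄))] / √(p1(1 − p1) + p0(1 − p0))}, with p̄ = 0.479.

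This gives (7.863 − 1.385)/0.541 = 11.97, so power exceeds 99.99%. The stated figure of approximately 99% is reproduced and is conservative.

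Other rates with 150 per arm:
- 50% versus 20%: (3.674 − 1.322)/0.640 = 3.67, power 99.99%.
- About 37% versus 15.8%: power about 99%.
- 30% versus 15.8%: power 83.7%.

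**2. Gain from stratifying.** From the SAP: 209 per arm and the planning rates. Assumed, because the visible text gives neither: baseline grades 2/3/4 at w = 30/40/30%, and a common slope in the log-odds of cure per grade in both arms. The pair 50% versus 20% is also an assumption. All outcomes are taken as observed.

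- Crude variance: [p1(1 − p1) + p0(1 − p0)]/n.
- Stratified variance: Σ w[p1k(1 − p1k) + p0k(1 − p0k)]/n + Σ w(dk − d)²/(2n), where dk is the difference in grade k and d is the overall difference.

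Worked case, 80% versus 15.8%, slope −1.0:
- The cure rates in grades 2/3/4 that average to the planning rates are 92.8/82.6/63.7% for TP-03 and 29.5/13.3/5.4% for vehicle.
- Crude: (0.1600 + 0.1330)/209 = 0.001402.
- Stratified: (0.1468 + 0.1239)/209 + 0.0021/418 = 0.001300.
- Reduction: 1 − 0.001300/0.001402 = 7%.

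| Rates | Slope | Variance reduction | 95% half-width, crude to stratified (points) |
|---|---|---|---|
| 80% vs 15.8% | −0.5 | 2% | 7.34 to 7.26 |
| 80% vs 15.8% | −1.0 | 7% | 7.34 to 7.07 |
| 80% vs 15.8% | −1.5 | 13% | 7.34 to 6.83 |
| 50% vs 20% | −0.5 | 3% | 8.68 to 8.55 |
| 50% vs 20% | −1.0 | 10% | 8.68 to 8.21 |
| 50% vs 20% | −1.5 | 20% | 8.68 to 7.78 |
| either | 0 | 0% | no change |

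A slope of −1.5 is an odds ratio of about 0.22 per grade, which is strong. A small simulation at the planning rates with 30% dropout and arm-specific imputation (two scenarios, 60 runs each) gave an SE about 1% lower when baseline was moderately prognostic, and no change when it was not. It is too small to do more than check the direction.

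**3. Effect on power.** At the planning rates power stays above 99.99%. At 30% versus 15.8% with 150 per arm, a variance reduction of 5 to 10% raises it from 83.7% to between 85.5% and 87.3%.

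**4. Number of imputations.** Let λ be the fraction of missing information, assumed 0.15 to 0.30. With complete-data variance W = 0.001402, total variance is T = W/(1 − λ), between-imputation variance is B = λT, and the Monte Carlo SE is √(B/m).

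- λ = 0.15: B = 0.000247; Monte Carlo SE 0.35 points at m = 20 and 0.16 at m = 100.
- λ = 0.30: B = 0.000601; 0.55 points at m = 20 and 0.25 at m = 100.
- Sampling SE √T: 4.1 to 4.5 points.
- Relative efficiency 1/(1 + λ/m) at λ = 0.30: 98.5% at m = 20 and 99.7% at m = 100.

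**The case against.** The strongest reply is that nothing here is an error. The unadjusted difference is valid under 1:1 randomization and matches the unadjusted test used for sizing. The size of the gain rests on a baseline mix and a prognostic slope that the documents do not give, and on complete data although the plan allows for 30% discontinuation. At the planning rates the gain is about 0.1 to 0.5 points of half-width around a difference of 64.2 points. All of this stands, and it makes the change an optional improvement. It does not remove the case for it: the baseline value is already collected, and with no association the large-sample cost is nil.

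Three stronger readings are tempting, and the documents do not support them.

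- A reader might infer that the plan ignores baseline grade altogether. It does not: baseline grade is in the arm-specific imputation model. Only the comparison omits it.
- A reader might infer that power is near 100% only at optimistic planning rates, so that the decision is at risk. Power is still 99.99% at 50% versus 20%, and about 99% down to a TP-03 rate of roughly 37% against 15.8%.
- A reader might infer that 20 imputations are too few because SAP Section 8.4 states "All percentages will be rounded to one decimal place". That is a display rule, and the seed is pre-specified. The efficiency lost is about 1.5% at λ = 0.30. By the same 0.1-point standard 100 imputations would also fail; meeting it needs about 250 to 600 (B/0.001²).

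**Conclusion.** The point holds as a low-cost refinement. The primary comparison is valid but leaves out a baseline variable that is already in the dataset and plausibly prognostic. Under the assumptions shown, stratification lowers the complete-data variance by about 2 to 13% at the planning rates and 3 to 20% at 50% versus 20%. The gain is zero if baseline grade does not predict cure, and the true figure cannot be derived from the documents. The benefit is a somewhat narrower interval and protection against chance imbalance in baseline grade. The primary decision is not expected to change at the planned effect; power would move noticeably only if the effect were far smaller, such as 30% versus 15.8%.

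The number of imputations is a side matter. Going from 20 to 100 reduces variation between seeds but does not materially change precision.

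**What to change.** Amend SAP Section 13.1 before unmasking:

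1. Within each imputed dataset, estimate the Mantel-Haenszel common risk difference stratified by baseline collarette grade (TABLES BASE*TRT*CURE with COMMONRISKDIFF). Pool the estimate and its SE with PROC MIANALYZE. Under 1:1 allocation the weights are close to the stratum shares, so the target remains the overall risk difference.
2. Fix a rule for sparse grades in advance: the minimum count, and the neighbouring grade with which a sparse one is merged. Apply it once to masked counts pooled over arms, so that the strata are the same in every imputed dataset.
3. Keep the crude difference as a supportive analysis.
4. Optionally set NIMPUTE=100.

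Do not simply carry this over to the secondary endpoints. Eradication needs baseline mite density categories. The composite needs a rule for combining baseline collarette and erythema grades without creating many small strata. If an adjusted analysis is wanted there, define those strata first.

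The cost is a few lines of SAS, including the output table and the pooling step, which currently selects the crude difference row. No new data, visits or subjects are needed, and the sample size stands.

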8.2 Missing or Inconclusive Data Handling

The primary efficacy analysis will be conducted with missing data and intercurrent events handled in the following manner:

- Discontinuation of study medication and non-optimal compliance is ignored [treatment policy strategy].
- Withdrawal due to lack of efficacy or AEs: missing data will be imputed as failure [hypothetical strategy].
- Missing data without withdrawal or withdrawal due to reasons other than lack of efficacy or AEs: missing data will be imputed employing Multiple Imputation (MI) using randomized treatment-based Markov Chain Monte Carlo (MCMC) methodology [hypothetical strategy].

In the event that the percentage of missing data due to discontinuation of study medication and non-optimal compliance exceeds 2%, these missing data will be imputed as failures and the primary efficacy analysis repeated in a separate analysis.

Sensitivity analyses on the primary efficacy endpoint are described in the Efficacy Analysis section.

Partial/missing start and end dates for AEs and concomitant medications will be imputed as follows:

Partial/missing start date:

- Dates with missing day only will be imputed as the 1st of the month unless the month and year are same as the month and year of first dose of study medication, in which case missing day will be imputed as the first dose day of study medication.
- Dates with both day and month missing will be imputed as 1 Jan unless the year is same as the year of first dose of study medication, in which case missing day and month will be imputed as the first dose day and month of study medication.
- Completely missing dates will be imputed as the first dose date of study medication unless the end date is on or before the first dose date of study medication, in which case missing date will be imputed as 1 Jan of the same year as the end date.

Partial/missing end date:

- Dates with missing day only will be imputed as the last day of the month unless the month and year are the same as the month and year of the last dose of study medication, in which case missing day will be imputed as the last dose day of study medication.

- Dates with both day and month missing will be imputed as 31 Dec unless the year is same as the year of the last dose of study medication, in which case missing day and month will be imputed as the last dose day and month of study medication.

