13.1.1.1 SENSITIVITY ANALYSIS I

The hypothetical strategy will be used for the intercurrent event. All missing data will be imputed assuming missing not at random (imputing from the vehicle treatment arm). The following SAS code will be used to generate the multiple imputation datasets:

```
PROC MI DATA=INDATA SEED=43623 NIMPUTE=20 OUT=MADATA MINIMUM=0 MAXIMUM=4  
ROUND=1;  
    BY TRT;  
    MCMC IMPUTE=MONOTONE;  
    VAR BASE DAY08 DAY15 DAY22 DAY43;  
RUN;  
PROC MI DATA=MADATA SEED=346238 NIMPUTE=1 OUT=OUT1 MINIMUM = . 0 0 0 0 0 MAXIMUM  
= . 4 4 4 4 4 ROUND = . 1 1 1 1 1;  
    BY _IMPUTATION_;  
    CLASS TRT;  
    MONOTONE REG(DAY08 = BASE/DETAILS);  
    MONOTONE REG(DAY15 = BASE DAY08/DETAILS);  
    MONOTONE REG(DAY22 = BASE DAY08 DAY15/DETAILS);  
    MONOTONE REG(DAY43 = BASE DAY08 DAY15 DAY22/DETAILS);  
    MNAR MODEL(BASE DAY08 DAY15 DAY22 DAY43 / MODELOBS=(TRT='Vehicle'));  
    VAR BASE DAY08 DAY15 DAY22 DAY43;  
RUN;
```

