13.1.1.2 SENSITIVITY ANALYSIS II

The hypothetical strategy will be used for the intercurrent event. All missing data will be imputed assuming missing at random (imputing from the same treatment arm as the subject with missing data) using similar code as provided in Section 13.1 for the primary efficacy analysis.

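### The primary imputation draws a 0–4 collarette grade from a bounded, rounded normal model and counts 0 as cure, so it imputes cure too rarely and pulls the treatment difference toward zero at the planned rates

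*SAP*

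**What the plan says.** SAP Section 13.1 imputes the primary endpoint by treatment arm with "PROC MI DATA=INDATA SEED=56636 NIMPUTE=20 OUT=OUT1 MINIMUM=0 MAXIMUM=4 ROUND=1" and an MCMC statement, which is a multivariate-normal model. The variables are the collarette grades at baseline and Days 8, 15, 22 and 43. No cure indicator is in the model; cure is derived afterwards: "The multiple imputation datasets will be used to calculate cure based on a collarette score of 0 at Day 43". Table 3 makes the grade a whole number from 0 to 4.

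Section 5 powers the trial "assuming a response rate of 80.0% in TP-03 and 15.8% for vehicle treatments", so most TP-03 subjects are expected at the bottom of the scale.

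Section 8.2 decides what reaches the imputation. One class does not: "Withdrawal due to lack of efficacy or AEs: missing data will be imputed as failure". The class that does is "Missing data without withdrawal or withdrawal due to reasons other than lack of efficacy or AEs".

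On volume, Section 5 allows for 30% discontinuation and explains why: "The planned enrollment is much greater than typically planned to achieve 300 completed subjects due to concerns regarding the impact of COVID-19", together with the possible loss of up to two sites.

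Sensitivity Analysis II (13.1.1.2) is run "using similar code as provided in Section 13.1 for the primary efficacy analysis". Sensitivity Analysis I (13.1.1.1) has the same limits and rounding, with a linear regression step, "MONOTONE REG(DAY43 = BASE DAY08 DAY15 DAY22/DETAILS". Sensitivity Analyses III to V do not use the normal model. Section 13.2 repeats the primary code for both secondary endpoints.

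**The concern.** With 80% of subjects at the lowest grade, the distribution is a spike at 0 with a short right tail. A normal distribution matched to its mean and SD puts about a third of its mass below 0. The range limit rejects those draws and redraws them inside 0–4, and many of the replacements round to 1 or more. Subjects who would have been cured are therefore imputed as not cured.

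The vehicle arm has the same defect, but with only 15.8% at 0 it loses far fewer points, so the two errors do not cancel. The primary difference is then understated, and its 95% CI is centred in the wrong place, even when data are missing completely at random, the easiest case for any imputation. Sensitivity I and II share the step, so their agreement with the primary result would give false reassurance.

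**Working it through.** **The plan's own figures.** With 150 per arm, 80.0% v 15.8% and one-sided 0.025, the two-proportion power formula gives more than 99.9%, consistent with the stated 99% or so. The true difference is 0.800 − 0.158 = 0.642. Randomizing 209 per arm to retain 150 implies (209 − 150)/209 = 28.2% missing, used here as the upper planning case.

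**Assumptions.** The documents give only the share at grade 0. The split of TP-03 grades 0/1/2/3/4 (%) is assumed and varied:
- grade-1-only: 80/20/0/0/0
- mild: 80/15/4/1/0
- middle: 80/12/5/2/1
- heavy: 80/8/6/4/2

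The SAP does not say whether the range is checked before or after rounding, so both orders were tried.

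**Closed form, no covariates.** With mean μ and SD σ, the probability that a draw ends at 0 is
- range checked before rounding: [Φ((0.5−μ)/σ) − Φ((0−μ)/σ)] / [Φ((4−μ)/σ) − Φ((0−μ)/σ)]
- range checked after rounding: the same, with −0.5 in place of 0 and 4.5 in place of 4.

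Middle split: μ = 0.12 + 0.10 + 0.06 + 0.04 = 0.32; σ = √(0.66 − 0.32²) = 0.747.
- Before: (0.595 − 0.334)/(1 − 0.334) = 0.39
- After: (0.595 − 0.136)/(1 − 0.136) = 0.53

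The target is 0.80.

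| TP-03 split | μ | σ | P(imputed 0), before / after |
|---|---|---|---|
| Grade-1-only | 0.20 | 0.400 | 0.67 / 0.76 |
| Mild | 0.26 | 0.577 | 0.50 / 0.63 |
| Middle | 0.32 | 0.747 | 0.39 / 0.53 |
| Heavy | 0.40 | 0.917 | 0.32 / 0.45 |

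For vehicle, an assumed split with mean 1.948 and SD 1.264 gives 0.073 / 0.105 against 0.158.

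**Effect on the difference.** If a fraction f is imputed in each arm, the expected difference is (1 − f) × 0.642 + f × (imputed TP-03 cure − imputed vehicle cure). Middle split:
- f = 0.10: 0.578 + 0.10 × (0.392 − 0.073) = 0.610 (before); 0.578 + 0.10 × (0.531 − 0.105) = 0.620 (after)
- f = 0.282: 0.461 + 0.282 × 0.319 = 0.551 (before); 0.461 + 0.282 × 0.426 = 0.581 (after)

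**Simulation of the specified code.** Settings: 209 per arm; five-visit ordinal data from a latent AR(1) normal with correlation 0.7 and assumed earlier-visit distributions; Day 43 missing completely at random, with dropout spread over four times, plus 3% intermittent missingness at Day 15; 20 imputations; Rubin's rules; 2000 runs per scenario. Entries are the mean difference (95% CI coverage), ranging over the two rounding orders.

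| Sent to MI | Grade-1-only | Mild | Middle | Heavy |
|---|---|---|---|---|
| 5% | 0.639–0.642 | 0.631–0.636 | 0.628–0.633 | 0.623–0.628 |
| 10% | 0.637–0.642 (95%) | 0.619–0.628 (93–94%) | 0.610–0.621 (90–94%) | 0.603–0.613 (87–92%) |
| 28% | 0.629–0.643 (95%) | 0.582–0.607 (75–90%) | 0.552–0.581 (50–76%) | 0.530–0.560 (27–59%) |

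Coverage was 94–95% throughout the 5% row. Imputed cure was 32–76% in TP-03 and 7–11% in vehicle. Changing the visit correlation to 0.5–0.85 in the middle split at 28% gave 0.551–0.586 (48–80%). The smallest z in any run was 7.7.

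**Alternatives under the same scenarios.** Sensitivity IV (observed data) gave 0.640–0.644 with about 95% coverage. Sensitivity V (missing as failure) gave about 0.58 at 10% and 0.46 at 28%.

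**Equal cure rates (15.8% in both arms), 4000 runs.** One-sided rejection was 2.3–2.5% with 10% missing in each arm, 2.7–3.0% with 10% TP-03 v 15% vehicle, and 3.3–5.4% with an assumed 10% v 30%.

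**The case against.** **The size is not in the documents.** Only the share at grade 0 is given; the grade splits, earlier-visit distributions and correlations are all assumed. If every non-cured TP-03 subject sits at grade 1, nothing material happens, even at 28% missing. This stands: the mechanism is certain, the size is conditional.

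**Modest missingness does little harm.** At 5% the shortfall is at most 1.9 points, about half of the complete-data standard error: √(0.80 × 0.20/209 + 0.158 × 0.842/209) = 3.7 points. The 28% case comes from an allowance for COVID-19 and site loss, and withdrawals for lack of efficacy or AEs never reach the imputation. This also stands, and makes 28% an upper case.

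**No decision changes.** Superiority at the planned effect is safe, and with similar missingness the error works against TP-03. At the planned rates the bias would reverse only if vehicle sent roughly 3 to 7 times as much data to MI. The inflated rejection rate needs equal cure rates and a strong imbalance; 2.7–3.0% is barely distinguishable from nominal at a Monte Carlo standard error of about 0.25 points. This stands too.

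**Other analyses would expose it.** Sensitivity III to V avoid the model. The COVID-19 set (Section 7.2) and the repeat with failures imputed when the 2% limit in Section 8.2 is exceeded would add further analyses. But these sit beside the primary result; none corrects the primary estimate or its CI.

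**Conclusion.** The concern holds: the code as written gives a wrong primary estimate even under missing completely at random. At the planned 80.0% and 15.8%, with similar missingness in the two arms, the bias is toward zero and grows roughly in proportion to the share imputed. If some TP-03 non-responders are above grade 1, the shortfall from 64.2 points is 0.6–1.9 points at 5% imputed, 1.4–3.9 at 10% and 3.5–11.2 at 28%. Coverage is near nominal at 5%, 87–94% at 10% and 27–90% at 28%. If all are at grade 1, the shortfall is at most 1.3 points.

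The test of superiority at the planned effect is not threatened. The harm is to the reported effect size and its interval. The secondary endpoints use the same step, but their bias was not simulated. This should be fixed before unmasking.

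**What to change.** - **Section 13.1:** use PROC MI with FCS, by arm, which also handles intermittent gaps. Impute Day 43 cure by logistic regression, or the 0–4 grade by cumulative logit, with baseline and earlier-visit grades as predictors. Remove MINIMUM, MAXIMUM and ROUND.
- **Sensitivity II:** make the same replacement.
- **Sensitivity I:** replace both the normal MCMC fill-in and the Day 43 linear regression, keeping the vehicle-based missing-not-at-random model.
- **Section 13.2:** write separate code for each endpoint, imputing eradication yes/no, and composite cure yes/no or its two component grades. The present code cannot be reused unchanged: Table 2 schedules no mite count at Day 8, yet the variable list includes it, and erythema (Table 4) stops at 3 while the code allows 4.
- Keep Sensitivity III to V.

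The cost is a few lines of SAS in Sections 13.1, 13.1.1.1, 13.1.1.2 and 13.2, with no new data. Sparse cells may need an augmented likelihood or fewer predictors. With the augmented likelihood, simulation at 10% and 28% missing (300 runs in each of six settings) gave a difference of 0.629–0.638 with 97% coverage. There was slight shrinkage: imputed cure was 78% v 80% in TP-03 and 17–18% v 15.8% in vehicle. That is mildly conservative. At around 5% missing the gain over the present code would be small.
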